In the setting of urogynecological procedures, the use of telephone follow up is an area that needs to be studied. There is no known standardization about how postoperative follow up visits are conducted after pelvic reconstructive surgery. There is much variation amongst providers concerning when and how postoperative follow up visits are completed. With the advances in robotic and laparoscopic procedures, hospital length of stay has decreased significantly. We now must examine the benefits of minimally invasive surgery as it relates to postoperative follow up. If in person postoperative visits can be replaced with telephone visits, we can possibly increase patient satisfaction. By allowing the patient to have a postoperative visit in the comfort of her own home, we can save her travel costs and travel time. Additionally, in our practice, the in person postoperative visits can ultimately be replaced with procedures and established patient visits, ultimately allowing for more availability for new patient consultations. By evaluating the use of telephone follow up, versus clinic follow up we will show that patient satisfaction with telephone follow up will be unchanged or improved compared to our standard practices.

II. Objective:

A. Primary Aim(s):

- To determine if patient satisfaction with postoperative care with telephone follow up is non-inferior to clinic follow up.

B. Secondary Aim(s):

- To determine if telephone postoperative follow up is a safe alternative to clinic postoperative follow up visits
- To determine if telephone or clinic follow up visits are preferred based on differing demographics (i.e. age, race, distance traveled, outpatient versus inpatient surgery).
- To determine length of visit differences between telephone and clinic follow up.

III. Hypothesis:

For the standard two-week postoperative visit, follow up telephone calls will be non-inferior to traditional office visits. The telephone visit is a safe and efficient alternative to the in person visit following urogynecological procedures.

a. H_0 Traditional office visits are superior to follow up via telephone calls for two-week postoperative visits.

IV. Interventions:

Scheduled telephone call at the two-week postoperative visit completed by the urogynecology clinic nurse.

V. Study Design:

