- Comparison of adverse events and Emergency Department (ED) visits between the two groups. Will be determined by reviewing the patient's record to identify adverse events as defined below. Informed consent will include consent to obtain outside ED records; as this is standard practice for patients seen in ED during perioperative/postoperative period.
- Actual time spent on phone call during postoperative telephone follow up compared to time spent in clinic follow up measured in minutes.
- Correlation, between groups, of overall patient's satisfaction with subjective measures, complications, demographics, and travel distance.

VIII. Data Collection:

At the initial visit, once eligibility status is determined and consent is obtained, data collection form will include demographics, distance traveled, complications, and number of ED visits, type of surgery performed etc. Also patients will complete three postoperative patient satisfaction questionnaires at the six-week postoperative clinic visit. This will include the Patient Satisfaction Questionnaire (PSQ) 18 Short Form, a validated questionnaire. Also will include the Patient Global Impression of Improvement (PGII), a validated questionnaire. And a three-question survey about patient satisfaction with the postoperative experience, not validated. All six -week visits will be in person. The questionnaires will be completed before the physician interviews the patient. These questionnaires will be stored in a locked filing cabinet and later transferred by the PI to an excel spreadsheet stored on a password-protected computer. Additionally, pertinent medical information will be extracted from the patient's medical chart, de-identified, and transferred to the an excel spreadsheet after surgery by a member of the study team, including socio-demographic data, perioperative and postoperative details, adverse events, and ED visits.

Adverse events are defined based on previous studies [4, 5,]

- bladder injury
- ureteral injury
- bowel injury

- operative estimated blood loss >500mL
- reoperation < 30 days
- hematoma
- pelvic abscess
- vaginal cuff cellulitis
- ileus
- small bowel injury
- transfusion
- pulmonary
- cardiac
- neurological injury
- urinary tract infection (culture proven, urinalysis with presence of leukocyte esterase, nitrites, or blood, symptoms of infection)
- pyelonephritis
- urinary retention (more than 6 week postoperative)
- mesh erosion
- incisional hernia
- wound complication

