- reoperation for complication of surgery
-

IX. Sample Size:

Sample sizes of 71 in Group 1 and 71 in Group 2 achieve 80% power to detect a non-inferiority margin difference between the group proportions of -0.12. The traditional office visit group proportion is 0.87. The Telehealth group proportion is assumed to be 0.75 under the null hypothesis of inferiority. The power was computed for the case when the actual Telehealth group proportion is 0.90. The test statistic used is the one-sided Z test (unpooled). The significance level of the test is 0.025.

X: Proposed Analyses:

Data analyses will be performed at the University of South Florida in Tampa, Fl. Data management and analyses will be conducted using SAS version 9.4 (SAS Institute, Inc, Cary, North Carolina). Subject demographic characteristics such as age, distance traveled, surgical procedures, ED visits will be summarized by standard descriptive statistics (e.g. means and standard deviations or median (range) for continuous variables and percentages for categorical variables. The difference between groups will be compared using the chi-square test or t-test, as appropriate. Logistic linear regression will be used to evaluate independent predictors for patient satisfaction. A p-value <0.05 will be considered statistically significant.

VIII. Confidentiality

At all times, appropriate measures will be taken to protect the confidentiality of all study participants in accordance with HIPAA guidelines. Patients will be approached for recruitment in private patient exam rooms. Once enrolled, all patients will be administered a study ID number starting with 1 and proceeding numerically. A master link between the individual subjects and their study ID number will be stored in a secure location (on a password-protected computer in the Urogynecology Fellows' office). All data collection forms (DCF) and stored patient information will only contain the study ID number. Charts will be reviewed in a secure location at all times. Upon completion of the data collection period, all information will be entered into an excel spreadsheet on a password-protected computer for data analysis.

IX Safety

This a voluntary study. Patients have the right to refuse to participate.

Data and Safety Monitoring

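### The satisfaction regression has about 16 expected events and probably seven or more terms, so ordinary maximum likelihood is fragile and Firth's penalised likelihood is a cheap, partial improvement

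*Combined protocol and SAP*

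**What the plan says.** Section X gives the secondary regression one sentence: "Logistic linear regression will be used to evaluate independent predictors for patient satisfaction". It then sets a 0.05 threshold for significance. It does not list the terms, say how the questionnaire becomes a binary outcome, name an estimator, or say what happens if a category contains no dissatisfied patients.

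Candidate predictors have to be gathered from elsewhere:

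- Section II.B asks about visit preference by "age, race, distance traveled, outpatient versus inpatient surgery".
- Section VII.B asks for a between-group correlation of overall "satisfaction with subjective measures, complications, demographics, and travel distance".
- Section X itself mentions surgical procedures and ED visits among the characteristics to be summarised.

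The expected event count is not stated, but Section IX supplies its ingredients: "Sample sizes of 71 in Group 1 and 71 in Group 2 achieve 80% power"; "The traditional office visit group proportion is 0.87"; and "The power was computed for the case when the actual Telehealth group proportion is 0.90".

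**The concern.** In logistic regression the information is limited by the rarer outcome, here dissatisfaction. With few events per term, two things go wrong with ordinary maximum likelihood. If a category has no dissatisfied patients, or only dissatisfied ones, its coefficient has no finite estimate (separation), and the analyst must decide after seeing the data whether to drop or merge it. Where estimates are finite, they tend to lie too far from zero, and likelihood-ratio tests can reject too often.

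At stake is the reliability of any reported predictors of satisfaction, since the plan will call terms significant at 0.05. The trial's main conclusion is not at stake.

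**Working it through.** **1. Reproduce the plan's sample size.** Inputs from Section IX: clinic 0.87, telephone 0.90, "non-inferiority margin difference between the group proportions of -0.12", one-sided 0.025, unpooled Z test, 80% power.

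n per arm = (1.960 + 0.842)² × (0.87×0.13 + 0.90×0.10) / (0.90 − 0.87 + 0.12)² = 7.849 × 0.2031 / 0.0225 = 70.85, rounded up to 71. Power at 71 is 80.1%. The figure reproduces.

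**2. Expected dissatisfied patients** (taking the Section IX proportions as proportions satisfied):

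- At the planning values: 71×0.13 + 71×0.10 = 9.23 + 7.10 = 16.3 (95% range 9 to 24).
- Both arms at 0.87: 18.5.
- Telephone at its null value ("The Telehealth group proportion is assumed to be 0.75 under the null hypothesis of inferiority"): 9.23 + 17.75 = 27.0.
- With 10% or 20% lost (64 or 57 per arm): 14.7 or 13.1. Section IX makes no allowance for loss, although Sections VI.B and VI.C exclude some patients after randomisation.

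**3. Events per term.** Arm, age, race, distance, inpatient/outpatient, complications and one subjective measure make seven terms if each takes one degree of freedom: 16.3/7 = 2.3. Ten terms give 1.6.

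**4. Simulated behaviour.** The documents give no prevalences or effects, so these are assumptions. Model: arm, age, race, distance, inpatient (40%), complication and ED visit; 11.5% dissatisfied; true log odds ratios 0.405 (age) and 0.693 (complication, an odds ratio of 2); 1,000 datasets per row. ML means use only datasets that did not separate; Firth means use all.

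| Race / complication / ED visit prevalence | N | ML separated or failed | Age: ML, Firth | Complication: ML, Firth |
|---|---|---|---|---|
| 20 / 10 / 5% | 142 | 50.1% | 0.442, 0.405 | 0.730, 0.669 |
| 20 / 20 / 10% | 142 | 21.8% | 0.470, 0.419 | 0.649, 0.639 |
| 30 / 30 / 20% | 142 | 4.4% | 0.476, 0.422 | 0.740, 0.690 |
| 40 / 40 / 40% | 142 | 0.6% | 0.449, 0.400 | 0.765, 0.691 |
| 20 / 20 / 10% | 114 | 31.4% | 0.465, 0.397 | 0.775, 0.703 |

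- **ML bias.** For age it is +9% to +17% (0.442/0.405 to 0.476/0.405). For complication it is −6% to +12% (0.649/0.693 to 0.775/0.693). With a complication odds ratio of 3 (log 1.099), ML gave 1.156 with seven terms and 1.216 with ten, or +5% and +11%.
- **Second simulation.** 3,000 datasets, 16.9 events on average, seven terms, race groups of 15% and 10%, complication 15%. ML separated or failed in 24.5%. Finite-fit means were 0.355 for a true 0.30 (+18%) and 0.575, 0.551 and 0.562 for a true 0.50 (+15%, +10%, +12%). Firth gave 0.307, 0.504, 0.491 and 0.493.
- **Type I error at 0.05, likelihood-ratio tests.** For a null complication term, ML rejected in 7.3% (seven terms) and 9.5% (ten terms), against 5.2% with Firth in both. For the continuous distance term the gap was smaller: 4.8% to 7.5% against 4.2% to 6.5%.

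**5. What Firth leaves or adds.**

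- At N = 142, mean predicted risk of dissatisfaction was 15% to 17% too high (relative) with seven terms and 20% to 21% too high with ten (for example 0.140 against 0.115 observed).
- Power for a complication odds ratio of 2 was 17% to 25%, and the 95% sampling range of that odds ratio was a factor of 3.1 to 5.1 either way.
- The median out-of-sample calibration slope was 0.33 to 0.39 (1 is ideal).
- Seven independent tests at 0.05 still carry a 1 − 0.95⁷ = 30% chance of at least one false positive.

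**The case against.** The strongest reply is that the seven-term model is not the plan's. Section X lists no terms, arm is nowhere named as a predictor, the list in Section II.B concerns preference for a visit type, and Section VII.B speaks of correlation. This stands to the extent that seven or more terms is an inference. It is still a fair one, because no other source tells the analyst what to enter. The wording in Section X could also mean linear regression of a score. The point assumes a binary outcome, which matches the proportions in Section IX.

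A reader might infer that the regression will often fail. The documents do not support that: they give no prevalences, and the failure rate runs from 0.6% to 50% depending on them.

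The bias comparison is also not entirely like for like, because ML means drop separated datasets and Firth means do not. In one further simulation, for a race group of 10% (true 0.50), ML averaged 0.58 over converged fits, Firth 0.66 on those same datasets, and Firth 0.48 over all. Some of the apparent inflation for rare categories is therefore selection. A real excess remains for age in that simulation (ML 0.348 against a true 0.30; Firth 0.310), but 0.05 is small beside a sampling SD of 0.32.

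Finally, a shorter model or merged categories would also help. That is true, and compatible with the change proposed.

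**Conclusion.** The point holds as a minor improvement to a secondary analysis. The roughly 16 events follow from the plan's own figures. About two events per term follows if seven or more terms are fitted. Under assumed prevalences, ordinary maximum likelihood then separates or fails in about 1% to 50% of datasets, overstates most non-zero log odds ratios by roughly 5% to 18% (partly through selection, and with one scenario at −6%), and has a type I error of about 7% to 10% for a sparse binary term such as complications.

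A reader might also infer that Firth's method fixes the analysis at no cost. It does not. It gives finite estimates and removes most of the coefficient bias, but it distorts predicted risks and leaves low power, wide intervals, overfitting and multiplicity in place. The distortion matters little while the aim is to identify independent predictors, because the plan proposes no predicted risks. Nothing here touches the primary non-inferiority test or the 71 per arm.

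**What to change.** In Section X, replace the regression sentence with wording such as: *Predictors of satisfaction will be assessed by logistic regression using Firth penalised likelihood (PROC LOGISTIC, FIRTH option), with profile-likelihood 95% confidence intervals and penalised likelihood-ratio p-values. Terms will be arm and the predictors named in Sections II.B and VII.B.*

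That sentence can be carried out only if the terms are written out, because the subjective measures and demographics are not defined. State the cut that defines a satisfied patient, the variables and their categories, and which sparse categories will be merged, all before the data are seen. Describe the results as exploratory. If predicted risks are reported, add an intercept correction.

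The cost is small: options in the SAS 9.4 software already planned and a short passage of text. No extra patients or data are needed.
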